Measurements will be taken pre-treatment, just after infusion (30-60 min post-infusion), half-way (210-240 min post-infusion), and at the end (450-480 min post-infusion) of the experiment. This design was selected to generate a robust set of richly collected psychometric testing data that can be analyzed over the full-time course of the experiment. In addition, the population PK/PD analysis method to be implemented (see below) will permit a “sharing” of information between subjects. This strategy will permit robust sampling of the psychological effects of each drug after a single dose, and relate these effects to the concentration of diphenhydramine.

Section 7.4: Pharmacokinetic Sampling Schedule/Design (Study Day 2)

All subjects will have PK samples drawn at the following time points from end of study drug administration:

PK Sample Time (min from end of administration)	Acceptable Range (min)
15	+/- 5
30	+/- 5
60	+/- 5
90	+/- 5
120	+/- 5
180	+/- 10
210	+/- 10
360	+/- 10
420	+/- 10
480	+/- 10

Additionally, a sample will be drawn at time 0 at 0-60 minutes prior to start of drug administration.

At time points where both PK samples are taken and psychometric testing is completed, the PK sample will be taken prior to the start of psychometric testing.

Given the limited population of PK data in the literature for diphenhydramine, a rich sampling scheme will be implemented for each subject. The frequent samples after the end of administration at 15, 30, and 60 min will capture the distributional phase of diphenhydramine. Furthermore, by richly sampling all 32 subjects, this will allow for adequate description of PK fixed effects (clearance, volume of distribution, etc.) and the corresponding inter-individual variabilities on each of those terms.

Section 7.5: Adverse Events (AEs)

Subjects will be under continuous observation at the study site. Both medical and nursing staff will be at the study site for the entire study day. Any subject reporting AEs during the study day will be medically evaluated as appropriate. All AEs and treatments will be recorded in the subject's study file. Serious adverse effects will be reported to the IRB according to IRB reporting policy. Subjects will be given direct phone numbers to report any adverse event after discharge from the study site.

SECTION 8.0: ASSESSMENTS

Section 8.1: Battery of Cognitive Function Tests

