The domains of cognitive function that will be measured will be reaction time, movement time, sustained attention, response latency, working memory, visual memory, short-term memory, and new learning. These domains of cognition will be measured before and serially after study drug administration as outlined in the protocol. The specific neuropsychometric tests that subjects will complete are Reaction Time, Rapid Visual Information Processing, Paired Associates Learning, Spatial Working Memory, and Digit Span (Appendix A). These tests have been developed for use in clinical trials by Cambridge Cognition Inc. to assess cognition as a drug safety measure. They have been shown to be sensitive to cognitive decline by pharmacological interventions, confirming their suitability for use in clinical trials to characterize negative effects on various domains of cognitive function.⁸ A Visual Analog Scale will also be used to assess sedation (Appendix A).

SECTION 9.0: ENROLLMENT AND CRITERIA FOR SUBJECT SELECTION

The study will consist of 32 healthy volunteers of any race or ethnicity. Sixteen subjects will be between the ages of 35 and 50 (Group A) and 16 subjects will be aged 65+ (Group B).

Section 9.1: Sample Size Calculation

The expected magnitude of the effect size for impairment and drowsiness is based on our previous work.(7) Taking into consideration the number of subjects that can be reasonably expected to complete the battery of psychometric exams, 32 subjects can be sampled at each of the given time points. Power was calculated using the pwr package in R (version 4.0.2). Using previously published information on cognitive effects of diphenhydramine, this design will result in a power > 0.8 to detect impairing effects of diphenhydramine, and > 0.9 to detect drowsiness effects from diphenhydramine.(7) For impairment, power was calculated at the type I error level of alpha = 0.05 for four sample groups (0, 30-60, 210-240, and 450-480 min) each with 32 subjects/samples and the previously established effect z-score of 0.45. The exact same procedure was used to calculate the power to observe changes in drowsiness scores, but using the previously observed effect z-score of 0.82.

Section 9.2: Females of Childbearing Potential

Females are considered to be of childbearing potential unless they meet one of the following criteria as documented by the investigator:

1. Post-menopausal for at least 1 year
2. Hysterectomy, bilateral oophorectomy, or salpingectomy

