
The PD endpoints, cognitive test result differences between Groups A and B and between baseline and post-diphenhydramine time points, will be assessed via one-way ANOVA with contrast. The PK endpoint will be assessed via one-way ANOVA with contrast of noncompartmental PK analysis. Patient AUCs will be numerically calculated based on patient-specific parameter estimates (i.e, the empiric Bayesian estimates) and compared between Groups A and B.

Section 10.2: Pharmacokinetic/Pharmacodynamic Modeling Strategy

The population PK modeling approach will be implemented using S-ADAPTM. In order to utilize available information in the literature, priors will be obtained for key PK parameters for diphenhydramine in order to leverage a maximum *a posteriori* estimation method. Previous PK studies will be used to supply prior information of the anticipated PK parameters expected from this study. A full step-wise covariate analysis will be done using log-ratio testing with a pre-defined significance level of alpha < 0.05 for forward selection and alpha < 0.01 for backward elimination. Concentrations below the limit of quantification will be handled using the Beal M3 method.

PK data from both Group A (subjects aged 35-50 years) and Group B (subjects aged ≥ 65 years) will be analyzed simultaneously. Patient age will be explored as a possible covariate on the disposition of diphenhydramine.

Intravenous data generated from this study and absorption data following intramuscular administration from literature data will be used to perform model estimates for intramuscular administration.

Continuous PD biomarkers (cognitive test results) will be handled accordingly, which will entail estimation of maximum effect (Emax) and corresponding blood concentrations for 50% of maximum effect (EC50). Categorical PD biomarkers (cognitive test results) will be handled using a hidden Markov method. This method will provide the probability of a patient being at a certain level given the concentration of the drug in the body. This approach has been used extensively to jointly model PK/PD for psychoactive substances.

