Subsequent simulation-based studies will be utilized to simulate the likely performance on psychometric testing given a dose, dosing interval, and infusion time. Clinical trial simulations, incorporating the inter-individual variability observed in this study, will provide recommendations for optimal dosing regimens given the desired psychometric outcomes for the majority of patients.

SECTION 11.0: ETHICAL AND REGULATORY CONSIDERATIONS

This study will be conducted according to good clinical practice guidelines, the Declaration of Helsinki, and the U.S. 21 CFR parts 50 and 56. Written informed consent for the study must be received from all participants.

SECTION 12.0: PARTICIPANT CONFIDENTIALITY

All information obtained during the conduct of the study with respect to the patient's state of health will be regarded as confidential in accordance with national data legislations. In order to maintain anonymity, patients will be identified by a special patient number in lieu of the patient's name in all patient data handling outside the study site. The patient log connecting the patient numbers to the identity of the patients will be kept by the Investigator, and will only be disclosed to external parties for the purpose of quality control, quality assurance, and at the request of the IRB. The participant code number and identifying information will be kept [REDACTED]

The results of the research may be published; however, the identifying information of subjects will be kept confidential.

A description of this clinical trial will be available on <http://www.ClinicalTrials.gov>, as required by U.S. Law. This website will not include information that can identify subjects. At most, the website will include a summary of the results.

A detailed study report with results and data generated from this research may be provided to [REDACTED] in a format which protects the confidentiality of study participants.

Laboratory specimens (CBC and CMP) will be sent to [REDACTED] for processing. Coded laboratory specimens (PK samples) will be sent to [REDACTED] for processing.

Coded data or specimens collected in this research might be used for future research or distributed to another investigator for future research without the consent of research subjects.

SECTION 13.0: RISKS

There will be risk associated with this study.

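### Section 10.2 bases regimen recommendations on simulations that name only inter-individual variability; no uncertainty in the fitted PK/PD parameters is stated, so simulated shares of patients can look firmer than they are

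*Combined protocol and SAP*

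**What the plan says.** Section 7.2 gives every subject 50 mg once, as a 5-minute bolus. Section 7.3 schedules one baseline and three post-dose test sessions: half of each age group at 30, 210 and 450 minutes, the other half at 60, 240 and 480.

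Section 10.2 fits Emax and EC50 to the continuous tests and a hidden Markov model to the categorical ones. Literature priors are planned for PK parameters only. The model is then used to "simulate the likely performance on psychometric testing given a dose, dosing interval, and infusion time". The section ends: "Clinical trial simulations, incorporating the inter-individual variability observed in this study, will provide recommendations for optimal dosing regimens", for most patients and relative to a desired psychometric outcome. Neither the outcome nor the majority is given a number.

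Section 7.4 argues that rich sampling will describe the PK fixed effects and their variability adequately. Section 7.3 has a qualitative PD rationale: staggered test times, and a population method that shares information between subjects. No section states a standard error, interval, bootstrap or parameter draw for the PD parameters or the simulations.

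**The concern.** Two kinds of uncertainty enter a simulated share of patients: how much patients differ, and how well the concentration-effect curve is known. Section 10.2 names only the first. If the second is left out, each regimen yields a single proportion without an interval, and a reader cannot tell a well-supported 60% from a poorly supported one.

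The design makes this matter. Dose, rate and interval are all simulation inputs, and none of them varies in the trial. Information about the curve comes only from falling concentrations after one dose and from differences between subjects. At stake are the EC50 estimate in the second objective of Section 2.0 and the regimen recommendations. The primary and secondary outcomes in Section 4.0 do not use Emax or EC50.

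**Working it through.** **The plan's own figure.** Section 9.1 uses a "previously established effect z-score of 0.45" for impairment; drowsiness power was calculated "using the previously observed effect z-score of 0.82". For a one-way ANOVA with 4 groups of 32 and alpha 0.05, reading these as Cohen's f gives power 0.993 and >0.999, consistent with the stated >0.8 and >0.9. Reading 0.45 as a largest difference in SD gives only 0.29-0.54, so f is the reading used here. These figures concern detecting an effect, not the precision of a curve.

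**Peak effect.** If one time point stands apart from three equal ones, f = d√3/4, so d = 4f/√3. This gives 4 × 0.45/1.732 = 1.04 SD and 4 × 0.82/1.732 = 1.89 SD.

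**From the documents.** 32 subjects × 3 = 96 post-dose sessions per test, at the six times above.

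**Assumed, not in the documents.** Terminal half-life 4 or 8 h; 15-minute distribution half-life with equal weights; 30% CV in concentration; concentrations known without error (favourable to the plan); within-subject correlation 0.5 or 0.8; EC50 at 0.3, 1 or 3 times C45, the typical 45-minute concentration; 40% CV in Emax between patients. Half-life, correlation and EC50 combine to 12 scenarios per peak effect.

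**Precision of the curve.** With E(C) = Emax·C/(EC50 + C), expected Fisher information and the delta method at 1.04 SD give:

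- SE of log EC50: 0.48-1.42. Since exp(1.96 × 0.48) = 2.6 and exp(1.96 × 1.42) = 16, EC50 is known to within a factor of about 2.6 to 16 either way.
- Relative SE r of the predicted effect: 0.10-0.16 at C45, 0.12-0.23 at 2 × C45 and 0.14-0.45 at 4 × C45.

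**From precision to a wrong majority.** Let the target be an effect below a threshold. A 40% CV is a log SD of √ln(1.16) = 0.385. If the true share meeting the target is 40%, the threshold lies 0.253 × 0.385 = 0.098 below the median on the log scale. A plug-in simulation reports a majority when the fitted effect is too low by more than that, with probability about Φ(−0.098/r). For a true share of 20% the distance is 0.842 × 0.385 = 0.324.

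| Exposure | 40% true: formula | 40% true: simulate and refit | 20% true: formula | 20% true: simulate and refit |
|---|---|---|---|---|
| C45 | 17-27% | 17-34% | 0-2% | 0-5% |
| 2 × C45 | 21-34% | 21-38% | 0-8% | 1-11% |
| 4 × C45 | 24-41% | 24-45% | 1-24% | 3-21% |

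The refit columns use 400 simulated trials per scenario. Repeat runs put the overall range for a true share of 40% at about 15-49%.

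**Where the exposures lie.** Under the assumed PK, the end-of-injection level is 1.9-2.0 × C45, but the first test is at 30 minutes. So 2 × C45 is about the highest level that the regimen produces, with no test session at it, and 4 × C45 is beyond it.

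**Other effect sizes, true share 40%.** The refit range over all three exposures is 11-36% at 1.89 SD and 29-46% at 0.45 SD.

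**A check without a PD model.** An observed 17 of 32 (53%) has an exact 95% interval of 34.7-70.9%. The lower limit first exceeds 50% at 23 of 32 (72%).

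**The case against.** The strongest reply has four parts.

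- *The use is exploratory.* Section 2.0 says the model will explore dose and rate, and Section 10.2 calls the simulations subsequent studies. The phrase "recommendations for optimal dosing regimens given the desired psychometric outcomes for the majority of patients" may describe a target population rather than a claim tested at 50%. This stands, and it limits the weight of the point. Section 10.2 nevertheless commits to recommendations.
- *The error rates depend on where the truth is placed.* This also stands. With a true share near 50%, any noisy estimate often crosses; at 20% the error at C45 is at most 5%. No PD values are in the documents, and the simulated time profiles put the peak implied by f = 0.45 at about 1.13-1.23 SD, so 1.04 SD is somewhat pessimistic.
- *The plan does argue for its PD data.* Section 7.3 does so, qualitatively. It gives no precision.
- *The modellers may carry parameter uncertainty anyway.* They may. The plan is silent on it and does not exclude it; if they do, the added wording costs nothing.

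A reader might infer that one dose makes Emax and EC50 inestimable. The documents do not support that: six post-dose test times and between-subject PK spread are pooled, so both are identifiable in principle. A reader might also infer that a majority should be claimed only when a lower 95% limit exceeds 50%. Nothing in the plan calls for such a rule, and it is a real trade-off. At 1.04 SD with a true share of 80%, it would still claim the majority in 66-96% of trials at C45, but in only 29-71% at 2 × C45 and 6-54% at 4 × C45.

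**Conclusion.** The point holds as one of omission and is worth considering. Section 10.2 promises regimen recommendations from simulations whose only named variability is between patients, and no parameter uncertainty is stated anywhere. That textual gap does not depend on any assumption.

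Its size does. Under the listed assumptions and a 1.04 SD peak, a wrong majority appears in roughly 15-49% of trials when the true share is 40%, and in 0-21% when it is 20%. These are illustrations, not forecasts for this trial. The gap covers the hidden Markov part as well, although only the Emax part was quantified. It would be wrong to read the point as undermining the trial's comparisons with baseline or between age groups.

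**What to change.** Add to Section 10.2:

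1. *PD parameters, including Emax, EC50 and the hidden Markov parameters, will be reported with 95% intervals (profile likelihood for Emax and EC50, with an unbounded limit reported as such).*
2. *Each simulation replicate will draw the PK and PD parameters from their joint estimated uncertainty in addition to inter-individual variability, and each simulated share of patients will be reported with a 95% uncertainty interval.*
3. *Results for regimens whose predicted exposure exceeds that of the studied regimen, or that involve repeated dosing, will be labelled model-based extrapolation.*

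The interval in item 2 is essential. Averaging the share over parameter draws is no cure: at 1.04 SD and a true share of 40%, the averaged share still exceeds 50% in 20-43% of trials. Item 3 is a label, not a prohibition.

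A linear concentration-effect comparator is optional. If used, the 5% boundary cut of 2.71 applies to twice the log-likelihood ratio.

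This is a cheap improvement: wording, extra refits for profiling and parameter draws, and wider, more modest statements about regimens. Objectives, sample size, visits and procedures do not change, and no dose or schedule is proposed.

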Appendix A: Battery of Cognitive Tests

See attached Paired Associates Learning (PAL), Digit Span (DGS), Reaction Time (RTI), Rapid Visual Information Processing (RVP), Spatial Working Memory (SWM), and Visual Analog Scales for Sedation Assessment.

Appendix B: Dent Policy & Procedure INF-024 for Intravenous Infusion of Diphenhydramine

See attached.

Appendix C: Informed Consent Process

See attached.
